10.3 Exploratory Analyses

10.3.1 Immunoglobulin

The number and percentage of subjects with detectable RABV-G-specific immunoglobulin ($> \text{LLOQ}$: IgM $\geq 780 \text{ U/ml}$, IgA $\geq 195.5 \text{ U/ml}$ and IgG $\geq 780 \text{ U/ml}$) levels will be determined for each visit and displayed by vaccination group and dose regimen including 95% exact confidence limits. The percentages will be based on subjects providing data for the respective visit.

For evaluation of values below the limit of quantification (=BLQ values) for tables and figures, the following conventions will be made:

- Values <LLOQ are identified as BLQ values.
- All concentration values marked as BLQ will be set to $0.5 * \text{LLOQ}$ (LLOQs: IgM 780 U/ml, IgA 195.5 U/ml, IgG $\geq 780 \text{ U/ml}$)
- Missing post-dose values will not be replaced.

Absolute (raw untransformed) RABV-G-specific IgM, IgG and IgA levels will be summarized for each visit by vaccination group and dose regimen.

RABV-G-specific immunoglobulin levels will be log-transformed and the mean and 95% confidence interval of the log-transformed values will be calculated. The GMTs (= antilog mean of log-transformed data) and the corresponding 95% confidence intervals for the GMTs (=antilog lower and upper 95% confidence bound of log-transformed data) as well as geometric SD, median, minimum and maximum will be tabulated by vaccination group and dose regimen for baseline and each postbaseline visit.

10.3.2 Cellular Immune Response

Cellular immune response results will be summarized using descriptive statistics by parameter, vaccination group, and visit. Changes from baseline will also be summarized. If only sparse data are available, the data may not be tabulated for single parameters, but listed only.

Peripheral blood mononuclear cell will not form part of this SAP and CSR analysis.

10.3.3 Cytokine assessment

Cytokine assessments will be summarized using descriptive statistics by parameter, vaccination group, and visit. Changes from baseline will also be summarized. If only sparse data are available, the data may not be tabulated for single parameters, but listed only.

10.3.4 Transcriptome Profiling

The results of transcriptome profiling will not be part of the trial database and are not subject to the statistical analysis.

10.3.5 Immune Receptor Sequencing

The results of immune receptor sequencing will not be part of the trial database and are not subject to the statistical analysis.

11. SAFETY ANALYSES

A description of the collection of safety assessments can be found in section 9.2 of the protocol.

11.1 Safety Endpoints and Variables

The analysis of the primary objective to assess the safety and reactogenicity profile will examine solicited and unsolicited adverse events.

The primary endpoints include the following:

- The percentages of subjects with, and the frequencies and intensities of solicited local AEs reported on the day of vaccination and the 7 subsequent days (Days 1-8).
- The percentages of subjects with, and the frequencies, intensities, and relationship to vaccination of solicited systemic AEs reported on the day of vaccination and the 7 subsequent days (Days 1-8).
- The duration (in days) of solicited local AEs, of solicited systemic AEs, and of the individual solicited AEs.
- The percentages of subjects with and frequencies and intensities of any unsolicited and related unsolicited AEs reported on the day of vaccination and the 28 subsequent days (Days 1-29).

- The percentages of subjects with and frequencies and relationship to vaccination of any serious AEs (SAEs) and any medically attended AEs (MAAEs) up to 12 months after the last dose.
- The percentages of subjects with and frequencies and relationship to vaccination of any AEs of special interest (AESIs) up to 12 months after the last dose.

Secondary safety endpoints are:

- The percentages of subjects with and frequencies of SAEs and MAAEs related to study vaccination from 12 months after the last dose up to 24 months after the last dose (trial end).
- The percentages of subjects with and frequencies and relationship to vaccination of any AESIs from 12 months after the last dose up to 24 months after the last dose (trial end).

Further safety variables include the following:

- Extent of exposure
- Physical examination, weight, BMI
- 12-Lead electrocardiogram
- Vital signs
- Safety laboratory - hematology, biochemistry, coagulation
- Laboratory - Urine dipstick pregnancy test, serum pregnancy test (human chorionic gonadotropin)

11.2 Adverse Events and Vaccination Site Reactogenicity Assessment

Definitions and procedures for recording, evaluating, follow-up, and reporting of AEs are provided in Appendix 11 of the protocol.

The intensity of AEs will be graded in the following manner:

Absent:	• Grade 0	• No AE
Mild:	• Grade 1	• An event that is easily tolerated by the subject, causing minimal discomfort and not interfering with everyday activities.
Moderate:	• Grade 2	• An event that causes sufficient discomfort to interfere with normal everyday activities.
Severe:	• Grade 3	• An event that prevents normal everyday activities. An AE that is assessed as severe should not be confused with a SAE. Severe is a category utilized for rating the intensity of an event; and both AEs and SAEs can be assessed as severe.

11.2.1 Solicited Adverse Events

Local (injection site pain, redness, swelling, and itching) and systemic (fever, nausea/vomiting, diarrhea, headache, fatigue, myalgia, and arthralgia) solicited AEs on the day of vaccination and the 7 subsequent days (Days 1 to 8, Day 8 to 15 [Rabipur Dose 2] and Days 29 to 36) will be collected on diary cards by the subjects.

By definition, all local solicited symptoms are considered related to vaccination.

AEs with individual AE term can be documented by the subject in the diary as other continuing general reaction with start and end date. If such an AE is documented in the diary, the investigator will also document it on the respective AE pages of the eCRF. It will then be analyzed within the unsolicited AEs documented there. The respective diary entries will only be listed.

Local and systemic solicited AEs will be assessed on an intensity scale of absent, mild, moderate, and severe. Direct data entries of mm for redness and swelling and °C for fever/temperature will be given. The following intensity grading for solicited AEs (day of vaccination and 7 subsequent days) will be applied:

Solicited AE	Grade*	Definition
Local AEs (reported in the subject diary as Injection Site Reactions)		
Pain at injection site	0	Absent
	1	Does not interfere with activity
	2	Interferes with activity and/or repeated use of non-narcotic pain reliever >24 hours
	3	Prevents daily activity and/or repeated use of narcotic pain reliever
Redness	0	≤2.5 cm
	1	2.5 – 5 cm
	2	5.1 – 10 cm
	3	>10 cm
Swelling	0	≤2.5 cm
	1	2.5 – 5 cm and does not interfere with activity
	2	5.1 – 10 cm or interferes with activity
	3	>10 cm or prevents daily activity
Itching	0	Absent
	1	Mild, no interference with normal activity
	2	Moderate, some interference with normal activity
	3	Significant, prevents normal activity
Systemic AEs (reported in the subject diary as General Reactions)		
Body Temperature	0	<38°C
	1	≥38°C – 38.4°C
	2	≥38.5°C – 38.9°C
	3	≥39°C
Headache	0	Absent
	1	Mild, no interference with normal activity

Solicited AE	Grade*	Definition
Fatigue	2	Moderate, some interference with normal activity and/or repeated use of non-narcotic pain reliever >24 hours
	3	Significant; any use of narcotic pain reliever and/or prevents daily activity
Chills	0	Absent
	1	Mild, no interference with normal activity
	2	Moderate, some interference with normal activity
Myalgia	3	Significant, prevents normal activity
	0	Absent
	1	Mild, no interference with normal activity
Arthralgia	2	Moderate, some interference with normal activity
	3	Significant, prevents normal activity
	0	Absent
Nausea/ Vomiting	1	Mild, no interference with normal activity
	2	Moderate, some interference with normal activity
	3	Significant, prevents normal activity
Diarrhea	0	Absent
	1	2 or 3 loose stools or <400 g/24 hours
	2	4 or 5 stools or 400 – 800 g/24 hours
	3	6 or more watery stools or >800 g/24 hours or requires outpatient i.v. hydration

*United States Food and Drug Administration toxicity grading scale; i.v. = intravenous.

Solicited AEs are also documented as AEs on the respective eCRF pages by the investigator, if they are serious and/or are ongoing on Day 8.

For every solicited AE, the maximum over all grades documented in the diary on the day of vaccination and the 7 subsequent days will be defined as grade (intensity) of this solicited AE.

Frequencies and percentages of local and systemic solicited AEs reported on the day of vaccination and the 7 subsequent days will be displayed by vaccination group, by subject overall and vaccination dose (number).

An overall summary table will display frequencies and percentages by grade (intensity) including any grade of:

- Any solicited AEs
- Local solicited AEs

- Systemic solicited AEs
- Related systemic solicited AEs
- Any solicited AEs ongoing on Day 8

Frequencies and percentages by grade (intensity), including any grade, will also be displayed for the individual terms of solicited AEs. Gradings of zero (AE is absent) will not contribute to the numbers tabulated.

The duration in days of a solicited AE will be represented by the number of days with diary entries of Grade ≥ 1 (out of Days 1-8) reported by a subject per solicited AE term and diary (corresponding to vaccination dose). Thus, the duration in days can range from 1 to 8 per prespecified solicited event term and vaccination dose administered.

The duration of Grade 3 solicited AEs will be derived by counting only days with Grade 3 entries.

For subjects without a specified event term, no duration of this event will be calculated, ie, no zero durations are possible.

The number of days of solicited AEs, as well as the number of days of solicited Grade 3 AEs will be tabulated with basic statistics by vaccination group and vaccination dose (number) for any solicited AE, any local solicited AE, any systemic solicited AE, any related systemic solicited AE, and the individual terms of solicited AEs.

In addition, frequency tables displaying solicited AEs by diary day, grade, vaccination group, and vaccination dose (number) will be prepared as well for any solicited AE, any local solicited AE, any systemic solicited AE, any related systemic solicited AE, and the individual terms of solicited AEs. These tables will show grade (severity) as: None (Grade 0), Any (Grades 1 to 3), Grade 1, Grade 2, and Grade 3.

The days of onset of solicited AEs will be displayed by frequency counts for any solicited AE, any local solicited AE, any systemic solicited AE, any related systemic solicited AE, and the individual terms of solicited AEs.

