5.8 Benefit-Risk Assessment

5.8.1 Possible Risks and Adverse IMP Reactions

No final clinical data for CV7202 are available to date.

Evidence from non-clinical studies shows that CV7202 is well-tolerated in relevant animal species and no safety risks have been identified.

The LNP-formulated RNAActive® rabies vaccine (CV7202) for i.m. administration is being tested for the first time in humans. As with every vaccination and based on previous clinical experience with other RNAActive® vaccines as well as preliminary data after administration of CV7202 to the first 10 subjects vaccinated with 5 µg of CV7202 in the current trial, local reactions, i.e. pain, redness, itching and swelling at the injection site, and systemic AEs, i.e. chills, fatigue, headache, fever, myalgia, arthralgia, nausea/vomiting and diarrhea, are expected side effects that typically resolve within 24 hours after the vaccination with or without corrective treatment with antipyretics [18, 19, 20, 21].

As for every vaccine, the occurrence of allergic/anaphylactic reactions cannot be excluded and emergency equipment for the treatment of such reactions must be available at the trial site. These events are unexpected and constitute a potential important medical risk. So far, no allergic/anaphylactic reactions have been observed in the completed and ongoing clinical trials after repeated administration of protamine-formulated RNActive® vaccines, nor after administration of CV7202 to the first 10 subjects vaccinated with 5 µg of CV7202 in the current trial.

During the very early stages of manufacture of CV7202, ampicillin is used. Although there is no evidence of residual ampicillin in the final investigational medicinal product (IMP), subjects with a previous class I allergic reaction to beta-lactam antibiotics should be excluded from vaccination with CV7202 as a measure of precaution.

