11.2.2 Unsolicited Adverse Events

Serious AEs, intercurrent medical conditions, AEs leading to trial or vaccine withdrawal, AEs of special interest (AESIs) and MAAEs will be collected by the investigator in the eCRF throughout the trial.

AEs with a suspected potential immune-mediated disease etiology will be considered AESIs. The investigator will assess if an AE is an AESI. A list of AESIs is provided in Appendix 10 of the protocol.

AEs that are reported as related to the test vaccine will be considered trial vaccine-related; missing classifications concerning trial vaccine relationship will also be considered trial vaccine-related.

Every unsolicited AE will be assigned to a vaccination dose (number) by consideration of the period of 28 days after vaccination administration. Unsolicited AEs can be assigned to either day 1 to 28 (dose 1 for any vaccination group), or day 29 to 57 (dose 2 for 2-dose regimens or dose 3 for the Rabipur group). For the Rabipur group, vaccination dose 2 is administered 8 days after vaccination dose 1, therefore no assignment of unsolicited AEs to vaccination dose 2 is done for the Rabipur group.

All AE summaries will be restricted to those AEs that occurred after the first administration of the trial product. Any other AE (ie, AE starting after trial entry and before the first vaccination) will be reflected only in the data listings. If it cannot be determined whether the AE occurred after the first administration of the trial product due to a partial onset date, then it will be counted as such. Verbatim terms in the eCRFs will be mapped to preferred terms (PTs) and system organ classes (SOCs) using the Medical Dictionary for Regulatory Activities (version 21.0 or higher).

The occurrence of unsolicited AEs reported on the day of vaccination and the 28 subsequent days will be presented. In addition selected AE summary tables will be repeated for unsolicited AEs occurring at any time after the first administration of the trial product.

Each AE summary will be displayed by vaccination group and dose regimen. Summaries by vaccination dose (number) will also be provided for all AEs. Summaries that are displayed by SOC and PT will be ordered by descending order of incidence of SOC and PT within each system organ class. Summaries will display number and percentage of subjects with at least 1 event and the number of events by vaccination group.

Summaries of the following types will be presented:

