- Overall summary of unsolicited AEs that contain an overview of each item below
- All AEs
 - Mild (grade 1) AEs
 - Moderate (grade 2) AEs
 - Severe (grade 3) AEs
- Related AEs
 - Mild (grade 1) related AEs
 - Moderate (grade 2) related AEs
 - Severe (grade 3) related AEs
- SAEs
- Related SAEs
- MAAEs
- AEs leading to withdrawal from study
- AEs leading to discontinued vaccination

- AESIs

Laboratory data will be graded by the site in the AE form according to the United States Food and Drug Administration toxicity grading scale and the Common Terminology Criteria for Adverse Events Version 5.0.

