16.2.7.1.1 Unsolicited Adverse Events - CRF Entries
Safety Analysis Set

Group: xxxxx

Complete subject code	Medical term of AE/ PT	Start date/ End date	Injection site/ time systemic reaction	AESI/ MAAE/ Outcome IC[a]	Action Intensity Relationship taken	Serial Comment
-----------------------------	---------------------------	----------------------------	--	------------------------------------	--	-------------------

&

\$ Post-vaccination adverse event
AESI = AE of special interest, MAAE = medically attended AE
[a] IC = Intercurrent

PROGRAM SOURCE: tlf-###, DATA CUT-OFF DATE: DDMMYYYY

RUN DATE: DDMMYYYY hh:mm

*Programming note:
Sort by start date and stop date within each subject.*

CureVac AG
CV-7202-104

Statistical Analysis Plan
24 February 2022

Sponsor
Protocol Number

Clinical Study Report
Page x of y

**16.2.7.1.2 Unsolicited Adverse Events - MedDRA Coding
Safety Analysis Set**

Group	Complete subject code	ID	Description	Low level term	Preferred term	High level term	High level group term	System organ class
-------	-----------------------	----	-------------	----------------	----------------	-----------------	-----------------------	--------------------

Adverse events were coded using MedDRA version 24.1.

PROGRAM SOURCE: tlf-###, DATA CUT-OFF DATE: DDMMYYYY

RUN DATE: DDMMYYYY hh:mm

Programming note: sort by ID within each subject.

CureVac AG
CV-7202-104

Statistical Analysis Plan
24 February 2022

Sponsor
Protocol Number

Clinical Study Report
Page x of y

**16.2.7.1.3 Serious Unsolicited Adverse Events
Safety Analysis Set**

*Programming note:
Repeat listing 16.2.7.1.1 for serious AEs. Include applicable SAE criteria data.*

CureVac AG
CV-7202-104

Statistical Analysis Plan
24 February 2022

Sponsor
Protocol Number

Clinical Study Report
Page x of y

**16.2.7.1.4 Unsolicited Adverse Events Leading to Trial or Vaccine Withdrawal
Safety Analysis Set**

Programming note:

Repeat listing 16.2.7.1.1 for AEs with taken = withdrawn from study or vaccination discontinued

CureVac AG
CV-7202-104

Statistical Analysis Plan
24 February 2022

Sponsor
Protocol Number

Clinical Study Report
Page x of y

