16.2.7.1.5 Deaths
Safety Analysis Set

Programming note:
Repeat listing 16.2.7.1.1 for serious AEs leading to death.

CureVac AG
CV-7202-104

Statistical Analysis Plan
24 February 2022

Sponsor
Protocol Number

Clinical Study Report
Page x of y

**16.2.7.2.1 Local Solicited Adverse Events
Safety Analysis Set**

Group: xxxxx

Complete subject code	Date of Injection site day 1 reaction	Measurement - Diary - Day Result	Ongoing Grade	afterReaction day 8	Medically serious	attended	Comment	Related
--------------------------	--	-------------------------------------	------------------	------------------------	----------------------	----------	---------	---------

PROGRAM SOURCE: tlf-###, DATA CUT-OFF DATE: DDMMYYYY

RUN DATE: DDMMYYYY hh:mm

Programming note: sort by symptom and diary day within each subject.

CONFIDENTIAL

CV-7202-104_Statistical_Analysis_Plan_V1.0.docm

CureVac AG
CV-7202-104

Statistical Analysis Plan
24 February 2022

Sponsor
Protocol Number

Clinical Study Report
Page x of y

**16.2.7.2.2 Systemic Solicited Adverse Events
Safety Analysis Set**

Group: xxxxx

Complete subject code	Date of day 1	General reaction	Measurement - Diary - Day	Result	Grade	Ongoing after day 8	Reaction serious	Medically attended	Comment Related
--------------------------	------------------	---------------------	------------------------------	--------	-------	------------------------	---------------------	-----------------------	--------------------

PROGRAM SOURCE: tlf-###, DATA CUT-OFF DATE: DDMMYYYY

RUN DATE: DDMMYYYY hh:mm

*Programming note:
Sort by symptom and diary day within each subject.*

CureVac AG
CV-7202-104

Statistical Analysis Plan
24 February 2022

Sponsor
Protocol Number

Clinical Study Report
Page x of y

**16.2.7.3 Vaccination Site Reactogenicity Assessment (Investigator)
Safety Analysis Set**

Group	Complete subject code	Visit	Visit Date	Time of assessment	Symptom / reaction	Measurement	Grade
-------	-----------------------	-------	------------	--------------------	--------------------	-------------	-------

PROGRAM SOURCE: tlf-###, DATA CUT-OFF DATE: DDMMYYYY

RUN DATE: DDMMYYYY hh:mm

*Programming note:
Sort by visit and symptom within each subject.*

CureVac AG
CV-7202-104

Statistical Analysis Plan
24 February 2022

Sponsor
Protocol Number

Clinical Study Report
Page x of y

**16.2.8.1 Hematology
Safety Analysis Set**

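### The any-MAAE primary endpoint is tabulated only among unsolicited AEs, and the SAP leaves open whether medically attended solicited reactions that end before Day 8 are counted

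*SAP*

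**What the plan says.** SAP 11.1 and Protocol 4.2 make MAAEs part of the primary endpoints. The SAP wording is "any medically attended AEs (MAAEs) up to 12 months after the last dose", and neither document excludes solicited reactions from it.

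SAP 11.2.1 explains how a diary reaction reaches the AE pages: solicited reactions are also "documented as AEs on the respective eCRF pages by the investigator, if they are serious and/or are ongoing on Day 8".

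SAP 11.2.2, the section on unsolicited events, states a broader collection duty: "AEs of special interest (AESIs) and MAAEs will be collected by the investigator in the eCRF throughout the trial". Protocol 9.2 has a matching duty for SAEs, MAAEs and AEs leading to trial or vaccine withdrawal up to 12 months after the last dose.

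MAAEs and AEs leading to discontinued vaccination are items under the heading "Overall summary of unsolicited AEs that contain an overview of each item below" in SAP 11.2.2. They have rows in shells 14.3.1.2.1 to 14.3.1.2.3 and 14.3.1.3.1, all of which are summaries of unsolicited AEs. The solicited summaries (14.3.1.1.1.1 onward) have rows by grade and for reactions still present on Day 8, and none for medical attendance.

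The solicited listings 16.2.7.2.1 and 16.2.7.2.2 do carry a column headed "Medically attended".

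**The concern.** The endpoint is defined over all MAAEs, but its only tables are built on unsolicited events. Whether a solicited reaction enters them depends on the transfer rule in SAP 11.2.1, and that rule does not mention medical attendance.

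The case is realistic. Protocol 5.8.1 says that local and systemic reactions to this vaccine "are expected side effects that typically resolve within 24 hours after the vaccination". Most would therefore end well before Day 8 and, if not serious, would meet neither named trigger. A fever or injection-site reaction that sent a subject to a doctor and settled within days is relevant to a tolerability profile, yet on the wording of 11.2.1 alone it would add nothing to the MAAE row.

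At stake is one component of the primary safety description, in groups small enough for a single subject to change the picture.

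**Working it through.** The plan states no figure for this point, so there is nothing to reproduce. The check traces one hypothetical event through the documents and then gives its scale.

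**Trace: a non-serious solicited reaction, medically attended, ending before Day 8**

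1. Endpoint (SAP 11.1): it qualifies as an MAAE.
2. Transfer rule (SAP 11.2.1): it is not serious and not ongoing on Day 8, so neither named trigger applies. By contrast, the same section sends other, non-prespecified reactions written in the diary to the AE pages without either condition.
3. Collection duty (SAP 11.2.2, Protocol 9.2): MAAEs are collected in the eCRF. This can be read as requiring an AE-page entry, but neither section says how it relates to step 2.
4. Tables: the MAAE row exists only in the unsolicited summaries. If step 2 governs, the event is not in them. If step 3 governs, it is.
5. Listings: it appears in 16.2.7.2.1 or 16.2.7.2.2 with its medically attended flag under either reading.

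The count therefore depends on which rule the site followed, while the listing does not.

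**Scale: one subject left out**

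The shells base percentages on all subjects in the vaccination group, so one omitted subject changes the rate by 100/n points. Planned group sizes (Protocol Table 8.1) are 16 at 1 µg, 16 at 2 µg, 10 at 5 µg and 10 on Rabipur.

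- n = 16: 100/16 = 6.25 points. 0/16 (exact 95% CI 0 to 20.6%) becomes 1/16 = 6.25% (0.2 to 30.2%).
- n = 10: 100/10 = 10 points. 0/10 (0 to 30.8%) becomes 1/10 = 10.0% (0.3 to 44.5%).

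SAP 6.4 reports 11 subjects vaccinated with Rabipur; there the step is 100/11 = 9.1 points. The intervals are Clopper-Pearson and show scale only.

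**Secondary trace: a solicited reaction that stops further vaccination**

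1. Protocol 5.1.2 bars a second CV7202 dose after a related grade 3 AE. It excepts six named systemic terms falling to grade 2 or below within 24 hours, and local reactions doing so within 48 hours.
2. What remains is narrow: a grade 3 reaction outside those exceptions, for example a longer-lasting one or a solicited term not among the six, that still ends before Day 8.
3. Listing 16.2.7.1.4 is specified as "Repeat listing 16.2.7.1.1 for AEs with taken = withdrawn from study or vaccination discontinued", so it draws on the AE-page listing. The solicited listings have no action-taken column.
4. Protocol 7.1 has the primary reason for stopping CV7202 recorded in the eCRF, so the information should exist outside both.

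**The case against.** The strongest reply is that SAP 11.2.1 never says these are the only triggers. SAP 11.2.2 and Protocol 9.2 impose a general duty to collect MAAEs and AEs leading to vaccine withdrawal. The visit procedures in Protocol 9.4 list both among the assessments during the solicited window. A site following those instructions could well have entered such reactions on the AE pages. What sites were told to enter is fixed by the annotated eCRF and the data management plan cited in SAP section 2, which are not available here. In a descriptive trial of about 52 subjects, a flagged reaction can also be read from a listing.

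Much of this stands. A reader might infer that medically attended reactions are certainly lost. The documents do not support that: the reactions are flagged and listed, and one reading of the collection duty puts them in the table. A reader might also infer a bias that grows with dose. The documents give no rate of such events by dose, so this is not shown.

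The reply does not settle the matter, however. The collection sentence in SAP 11.2.2 sits under unsolicited events, refers to the eCRF rather than the AE pages, and is not tied to 11.2.1. A listing is also no substitute for the tabulated percentage that defines a primary endpoint.

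On stopped vaccination the reply is stronger. That count is neither a primary nor a secondary endpoint. Group 2 (5 µg) has no second dose, so a loss of 1 in 10 cannot arise there. SAP section 7 analyses by the regimen actually received, so a subject denied Dose 2 is not among the eight in a two-dose column, and 1 in 8 does not apply either.

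**Conclusion.** The point holds as an unreconciled rule and a missing tabulation in a primary endpoint; loss of data is not shown. As written, the plan permits a non-serious, medically attended solicited reaction that resolves before Day 8 to be listed but not counted as an MAAE.

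Its size depends on the number of such reactions, which the documents do not give. Each affected subject would move a group rate by 6.25 points (n = 16) or 10 points (n = 10), assuming that the subject has no other MAAE in the table and that the transfer rule was applied literally. If sites entered every MAAE on the AE pages, the count is already complete and only the text needs clarifying.

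For discontinued vaccination the gap is secondary. It concerns only subjects due a further dose: the planned eight in each of Groups 3a and 4a, and the Rabipur group.

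**What to change.** 1. Reconcile SAP 11.2.1 with 11.2.2 by stating whether a medically attended solicited reaction belongs on the AE pages, and which source prevails for the MAAE count.
2. Derive any MAAE from the AE pages plus every solicited reaction flagged as medically attended in the diary data. Match the two sources so that a reaction recorded in both is counted once, because the shells report events as well as subjects.
3. Add solicited and unsolicited sub-rows under MAAEs in shells 14.3.1.2.1 to 14.3.1.2.3 and 14.3.1.3.1, and adjust the titles to match. SAP 11.2.2 assigns no unsolicited AE to Rabipur Dose 2, so state where a reaction from that diary is placed in the by-dose tables.
4. As a secondary change, for subjects due a further dose, extend listing 16.2.7.1.4 and the discontinued-vaccination row to any solicited reaction recorded in the eCRF as the reason vaccination was stopped.

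Rewriting the eCRF transfer rule for future data entry would achieve nothing. The SAP is dated 24 February 2022, and SAP 6.4 reports that the second interim analysis had already followed 53 vaccinated subjects to Day 57, past the last solicited window (Days 29 to 36).

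The cost is SAP wording, minor programming and possibly slightly higher reported rates. The medically attended flag is already among the listed data.
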